9.2 Sample Size Determination

The sample size for this study is based upon change from baseline for mean number of micturitions/24 hours within a single treatment arm. Change from baseline will be tested to determine if the change is different from zero i.e., a change in mean number of micturitions/24 hours. When the sample size is 125, a single group t-test with a 5% two-sided significance level will have 80% power to detect a change of 0.9 micturitions with a SD of 3.562 [Neurourology and Urodynamics, 2015]. Assuming 25% of the subjects will drop out, about 166 subjects will be enrolled to yield 125 evaluable subjects in 50 mg group.

9.3 **Populations for Analyses**

Population	Description
Enrolled	All subjects who sign the ICF.
Randomized	All subjects who are randomized. Subjects will be analyzed according to the study treatment to which they are randomized.
Full Analysis Set	The FAS will consist of all subjects who are randomized and receive at least 1 dose of IP and have at least 1 post baseline measurement for mean number of micturitions per 24 hours. The FAS will be analyzed by treatment arm as randomized (i.e., treatment arm based on randomization assignment). This will be the primary analysis set for efficacy analyses.
Safety Analysis Set	The SAF will consist of all subjects who took at least 1 dose of IP. The safety set will be analyzed by treatment arm as treated (i.e., based on the treatment the subject actually received rather than the treatment to which the subject was randomized).

The following populations are defined:

FAS: Full Analysis Set; ICF: informed consent form; IP: investigational product; SAF: Safety Analysis Set.

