#### 2.1.1 Estimand

The estimand of most clinical importance for this study is defined by the following four attributes:

- Target population: all subjects who took at least 1 dose of the study drug, and in whom a nonmissing measurement for mean number of micturition per 24 hours at baseline and after administration of the study drug is available.
- Outcome measurement: micturition frequency per 24 hours prior to switching (if switching occurs).
- Intercurrent events:
  - Dose escalation.
- Population-based summary: change from baseline to week 12/end of treatment (EoT) in micturition frequency per day within dose groups.

For this study, the treatment estimand is considered appropriate because of the fact that the response of subjects prior to switching is of primary interest. i.e., the estimate for 50 mg of mirabegron should be estimated from subjects who were randomized to 50 mg and the estimate for 25 mg should be estimated from subjects who were randomized to 25 mg while they were treated with 25 mg.

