### 6.4.1.1 Primary Analysis for Primary Efficacy Endpoint

The primary estimator for the primary estimand as defined in [Section 2.1.1 Estimand] will be calculated according to the evaluation of the primary efficacy endpoint. The primary efficacy endpoint will be analyzed using a Mixed Models Repeated Measures (MMRM). The MMRM model will include visit (the repeated term), treatment group (25 mg [total] or 50 mg [as-randomized]), pooled site, sex and the interaction between treatment group and visit as fixed effects and baseline measurement (the mean number of micturitions per 24 hours) as covariate. The algorithm to pool sites will be generated and documented prior to data base lock (Appendix 9.1). If the inclusion of pooled sites creates modeling problems, then dropping that factor will be considered. Subject will be identified as subject in the repeated statement.

The hypothesis for comparisons is given as follows:

- H0: The adjusted mean change from baseline at week 12 in mean number of micturitions per 24 hours in the 50 mg group is not different from zero.
- H1: The adjusted mean change from baseline at week 12 in mean number of micturitions per 24 hours in the 50 mg group is not equal zero.

Statistical testing will be done 2-sided at a 5% significance level.

The MMRM model results will be presented by treatment least squares (LS) means ( $\pm$  standard error [SE]) along with 2-sided 95% confidence intervals (CIs) and associated p-value for mean changes from baseline at weeks 4, 8 and 12 (the primary endpoint). Data from subjects who switch from 25 to 50 mg mirabegron will not be included in MMRM model. Data from those subjects prior to switching will still be included in the MMRM model with treatment equal to 25 mg.

Model fitting will be visually assessed. A scatter plot of residuals versus predicted values, along with histogram and normal probability plots will be produced.

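### The primary one-arm test uses a standard error conditional on the observed baselines, so for the population mean change it is too small, by an amount the documents do not let us fix

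*SAP*

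**What the plan says.** SAP 6.4.1.1 fits one MMRM to both arms, with change from baseline as the response. Baseline enters the model in this way: "baseline measurement (the mean number of micturitions per 24 hours) as covariate". The other terms are visit, dose group, pooled site, sex and dose group by visit.

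The null hypothesis concerns one arm only. It holds that the adjusted week-12 mean change "in the 50 mg group is not different from zero". The test is two-sided at 5%. On reporting, the SAP says: "The MMRM model results will be presented by treatment least squares (LS) means". Each comes with its SE, 95% CI and p-value. The SAP does not say at which baseline value the LS mean is taken, how sites and sexes are weighted, or whether the SE allows for sampling of baseline.

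Two other places bear on the target. The estimand in SAP 2.1.1 summarises "change from baseline to week 12/end of treatment (EoT) in micturition frequency per day within dose groups". Protocol 9.2, repeated in SAP 3, rests the size of the 50 mg arm on a different test: "a single group t-test with a 5% two-sided significance level will have 80% power". The planned change there is 0.9 and the SD is 3.562.

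**The concern.** An LS mean is usually evaluated at the sample mean baseline, and its model SE treats that mean as a known constant. Change is week 12 minus baseline, so baseline is part of the response and will generally correlate with it. A different sample of patients would have a different mean baseline and so a different mean change. That variation belongs in the error of an estimated population mean change.

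In a comparison of 50 mg with 25 mg the term drops out, because both LS means use the same baseline value. Here the primary hypothesis has no comparator, so nothing removes it. The single-group t-test behind the sample size does include it, through the full SD of change. The design and the analysis thus attach different error terms to the same claim.

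At stake are the width of the primary CI and the true level of the only primary test, which SAP 2.2 links to licence renewal.

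**Working it through.** **1. The plan's own figure.** One-sample t-test, n = 125, change 0.9, SD 3.562, two-sided 5%: the noncentral t distribution gives power 80.04%. With 25% dropout, 125/0.75 = 166.7 against the stated figure of about 166; 166 × 1.5 = 249. The sizing reproduces. The SE it implies is 3.562/√125 = 0.319.

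**2. The two variances.** Let s = 3.562, n50 = 125 and N = 249 × 0.75 ≈ 187 in both arms, so n50/N ≈ 2/3. Let R² be the squared correlation of baseline with change. Site and sex are left out until step 5.

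- Model variance of the LS mean: s²(1 − R²)/n50
- Variance with baseline random: s²(1 − R²)/n50 + s²R²/N, where s²R² = slope² × baseline variance
- SE ratio: √(1 + (2/3) × R²/(1 − R²))
- Actual level: 2 × (1 − Φ(1.96/ratio))

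With n50/N = 2/3 the second variance equals (s²/n50)(1 − R²/3), while the model reports (s²/n50)(1 − R²). So two thirds of the apparent precision gain from adjusting for baseline is not real, whatever R² is.

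**3. Which R² to assume.** Neither document gives R², a baseline SD or a baseline-to-week-12 correlation ρ. If baseline and week-12 variances are equal, R² = (1 − ρ)/2.

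**4. Results.** The last column simulates a three-visit MMRM with unstructured covariance, 125 and 62 subjects, complete data, an assumed correlation of 0.6 between post-baseline visits, and no site or sex terms. It used 3,000 runs per row, so the Monte Carlo SE near 5% is √(0.05 × 0.95/3000) = 0.4 points.

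| R² | ρ | Model SE | Correct SE | Ratio | Level, formula | Level, MMRM simulation |
|---|---|---|---|---|---|---|
| 0.05 | 0.9 | 0.311 | 0.316 | 1.02 | 5.4% | not run |
| 0.1 | 0.8 | 0.302 | 0.313 | 1.04 | 5.9% | 6.0% |
| 0.2 | 0.6 | 0.285 | 0.308 | 1.08 | 7.0% | 7.0% |
| 0.3 | 0.4 | 0.267 | 0.302 | 1.13 | 8.4% | 8.2% |
| 0.4 | 0.2 | 0.247 | 0.297 | 1.20 | 10.3% | 9.7% |
| 0.5 | 0 | 0.225 | 0.291 | 1.29 | 12.9% | 13.2% |

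Example at R² = 0.3: ratio² = 1 + 0.667 × 0.429 = 1.286, ratio 1.134, 1.96/1.134 = 1.73, level 8.4%. The 95% half-width (1.96 × SE) goes from 0.52 to 0.59 at R² = 0.3, and from 0.59 to 0.61 at R² = 0.1.

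**5. Site weights.** In an ANCOVA simulation with very unequal sites, LS means that weight sites equally gave 5.5%, 5.8%, 6.7% and 7.6% at R² = 0.1, 0.2, 0.3 and 0.4. With weights proportional to site size the inflation was about the same as with no site term.

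**6. Two checks on the cause.** With baselines held fixed across simulated trials, the level was 4.9 to 5.1%. With slope² × baseline variance / N added to the LS-mean variance, it was 4.8 to 5.1% (ANCOVA, R² 0.1 to 0.4), 4.6 to 5.2% (equal-weight sites, same range) and 4.6 to 5.9% (MMRM, R² 0.1 to 0.5).

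**7. Power.** With the corrected SE and a true change of 0.9, the normal approximation gives 82% at R² = 0.1, 85% at 0.3 and 87% at 0.5.

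**The case against.** The hypothesis speaks of an adjusted mean change. If that means the mean change for patients with exactly this sample's baselines, the planned test holds 5%, as step 6 shows. The SAP never states that target. A within-dose-group estimand, an objective about Chinese subjects and sizing on the full SD of change all point to the population mean. The ambiguity is real, but it is a reason to state the target rather than to leave the SE alone.

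A reader might infer that the primary test is shown to run at 6 to 13%. The documents do not support that. The range needs R² from 0.1 to 0.5, which they do not supply, and under equal variances the top end needs zero correlation between a subject's own baseline and week-12 counts. Entry also requires at least 8 micturitions per 24 hours. If that makes the baseline SD 0.8 of the week-12 SD, with ρ of 0.5 to 0.6 (all assumed), R² is about 0.06 to 0.11 and the level about 5.5 to 6%. Equal weighting of unequal sites lowers the inflation as well.

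A reader might also infer that the trial is too small. It is not: the sizing used the larger error term.

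Finally, SAP 6.1 and 6.4.1.2 plan the raw mean change with its SEM, which already contains the baseline term, so the discrepancy would be visible. That helps a careful reader but does not correct the primary p-value or CI. The absolute effect is modest: 0.02 to 0.07 micturitions on the half-width, against a planned change of 0.9.

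**Conclusion.** The point holds in a limited form. For the population mean change, the usual LS-mean SE is too small for any R² above zero, and the error always runs in the optimistic direction. Assuming equal variances and ρ of 0.4 to 0.8 (R² 0.1 to 0.3), the nominal 5% test runs at about 6 to 8.5% and the correct SE is 4 to 13% larger. With equally weighted, very unequal sites the same R² range gives 5.5 to 6.7%. An R² near 0.05 gives 5.4%, and 13% is reached only at R² = 0.5.

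These figures rest on the assumed correlations, on the LS mean being taken at the overall mean baseline with the ordinary model SE, and on simulations with complete data. A large effect would stay significant either way. A borderline result might not, and the reported interval is too narrow in both cases.

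**What to change.** In SAP 6.4.1.1:

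- State that the target is the mean change in the population represented by the 50 mg arm, not the mean change at this sample's baselines.
- Name the baseline value at which the LS mean is taken (the subject-level mean over both arms) and the weights for pooled site and sex.
- Keep the planned MMRM, but compute the primary SE, CI and p-value after adding slope² × baseline variance / N to the LS-mean variance, where N is the number of subjects in that mean baseline. A bootstrap of whole subjects, or a longitudinal model with baseline as a response, would serve equally well.
- As a sensitivity analysis, report the one-sample t-test used for sizing.

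The cost is a few lines of SAP text and minor programming. The fitted model does not change and no further subjects or data are needed. SAP 1 allows revisions until database hard lock; after lock, the corrected interval can be reported beside the planned one, with the reason. The downside is a slightly wider primary CI: 4 to 13% for R² of 0.1 to 0.3.

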# 2.3 Randomization

Subjects will be randomized in a 2:1 ratio to 50 mg mirabegron and 25 mg mirabegron using a computer-generated randomization Interactive Web Response System (IWRS). All consented subjects who meet the eligibility criteria will be randomized through IWRS. This service is set up prior to the study to allow the sites real-time allocation of the treatment to the next eligible subject based on the specifications and algorithm provided in the Randomization Specification Document. At visit 2/week 0 (baseline), subjects will be assigned a randomization number in accordance with the randomization code generated by the sponsor's designee.

Subjects will be assigned a subject number at study entry (i.e., signing the Informed Consent Form (ICF)). The subject numbers will be sequential and rising. The subject number will comprise of a 5-digit clinical unit number and 5 digit screening number.

Subjects will be randomized to receive IP according to the randomization schedule obtained via the IWRS system. The study site personnel will dispense the treatment according to the IWRS system's assignment. Specific procedures for randomization through the IWRS system are contained in the study procedures manual.

An enrolled subject who withdraws or discontinues before dosing or before randomization will be considered a screen failure. Randomized subjects who withdraw or discontinue will not be replaced.

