# **3** SAMPLE SIZE

The sample size for this study is based upon change from baseline for mean number of micturitions/24 hours within a single treatment arm. Change from baseline will be tested to determine if the change is different from zero i.e., a change in mean number of micturitions/24 hours. When the sample size is 125, a single group t-test with a 5% two-sided significance level will have 80% power to detect a change of 0.9 micturitions with a SD of 3.562 [Neurourology and Urodynamics, 2015]. Assuming 25% of the subjects will drop out, about 166 subjects will be enrolled to yield 125 evaluable subjects in 50 mg group.

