## 9 APPENDICES

### 9.1 **Pooling of Sites Algorithm**

Two hundred and forty-nine (249) subjects were randomized at 15 sites. When "site" is included as a factor in a statistical model, sites that have less than 8 FAS subjects in total will be identified and then combined for statistical analysis purposes according to the following algorithm:

- Step 1: Divide the sites into two groups with Group 1 including all sites that have at least 8 FAS subjects and Group 2 including all remaining sites. Sort each group in ascending order by total sample size and site number.
- Step 2: Starting at the top of the Group 2 list (i.e., the first site with the smallest total sample size), combine the minimum number of sites required to achieve a "pooled site" that has at least 8 FAS subjects in total. Continue forming "pooled sites" in this manner until all Group 2 sites have been grouped or it is no longer possible to form a "pooled site" with at least 8 FAS subjects in total.
- Step 3: If there is a site (or several sites) left after step 2, combine the site(s) with the last "pooled site" that is created. For the situation where no previous "pooled site" is created, combine the site(s) with the first site on the sorted Group 1 list.
- "Pooled site" will be assigned names PoolSite01, PoolSite02, etc. For sites not
  needing to be pooled, the original site name will be used such as Site001. For all sites
  that have been combined into pooled sites, the assigned pooled site will be used
  instead of the original site identification in all statistical models that include "site" as
  a factor. However, the original site identification will be used in all summaries of
  subject disposition or discontinuation by site and in all data listings.

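### The primary one-arm LS mean is tested against zero without stated weights for pooled site and sex; the usual equal-level default could cost power and shift the target if either is unbalanced

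*SAP*

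**What the plan says.** SAP 6.4.1.1 fits an MMRM with visit, treatment, pooled site, sex and treatment-by-visit as fixed effects and baseline as covariate. The null hypothesis is that the adjusted mean change at week 12 in the 50 mg arm is zero. "The MMRM model results will be presented by treatment least squares (LS) means", with SE, 95% CI and p-value. No weighting of the site and sex levels is given there. SAP 6.1 names SAS 9.4 or higher but no procedure or LS-mean option.

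SAP 9.1 sets the site levels: "sites that have less than 8 FAS subjects in total will be identified" and combined until each pool reaches 8. It records 249 subjects at 15 sites. If pooled site causes modelling problems, 6.4.1.1 allows it to be dropped.

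The sizing (Protocol 9.2, SAP 3) is for a simple mean. With 125 evaluable subjects, the SAP states that "a single group t-test with a 5% two-sided significance level will have 80% power"; the assumed effect is 0.9 micturitions and the assumed SD is 3.562. On dropout: "Assuming 25% of the subjects will drop out, about 166 subjects will be enrolled to yield 125 evaluable subjects in 50 mg group". Neither document gives site sizes or the expected share of women.

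**The concern.** An LS mean is a weighted average of model predictions over the levels of the class effects. Without an observed-margins option, SAS gives each level the same weight, so an 8-subject pooled site counts as much as the largest site and the sexes count 50:50. This model has no site or sex interaction with treatment, so a 50 mg versus 25 mg difference would be unaffected. The primary test, however, compares one arm's mean with zero, and the weights enter the estimate, SE, CI and p-value directly.

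Two things are at stake.

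- **Precision.** The sizing assumes the SE of a simple mean. Giving extra weight to small levels raises it.
- **Target.** SAP 2.1.1 defines the estimand over treated subjects with baseline and post-baseline data, summarised within dose group. An equally weighted LS mean answers for a different mix of those subjects. Dropping pooled site under the 6.4.1.1 fallback would then also change which mean is estimated.

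**Working it through.** **1. The plan's own figure.** SE = 3.562/√125 = 0.3186. Noncentrality = 0.9/0.3186 = 2.825. With 124 df, critical t = 1.979 and power = 80.04%; n = 124 gives 79.7%. The 125 reproduces. Dropout: 125/0.75 = 166.7, against the stated 166.

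**2. Where the extra variance comes from.** A hand calculation using week-12 completers only: N = 187 (125 in the 50 mg arm and 62 in the 25 mg arm), K pooled sites of size N_k, female share f. It assumes 2:1 allocation and the same sex share in every site. For the equally weighted 50 mg LS mean:

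Var/σ² ≈ (1/K²)Σ(1/N_k) + (1/3)²(1/125 + 1/62) + (0.5 − f)²/[N f(1 − f)]

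- Equal sites, f = 0.5: 1/187 + 0.00268 + 0 = 0.00803. The plan has 1/125 = 0.00800, so the SE ratio is 1.00.
- Equal sites, f = 0.8: the third term is 0.09/(187 × 0.16) = 0.00301. Total 0.01104; SE ratio √(0.01104 × 125) = 1.17.
- One site of 137 and fourteen of 8 (sum 249), scaled by 0.75 to 102.75 and 6, f = 0.5: the first term is (14/6 + 1/102.75)/225 = 0.01041. Total 0.01309; SE ratio 1.28.

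With observed-margin weights the first term is 1/187 and the third is zero in every layout, so the ratio stays at 1.00.

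**3. Under the planned MMRM.** The completers-only formula overstates the loss, because the MMRM also uses weeks 4 and 8. The generalised least squares variance was therefore computed for the SAP model, averaged over 40 random layouts per scenario. Inputs from the documents: 249 subjects, 2:1 allocation, 25% missing at week 12, SD 3.562. Assumed: site sizes, female share, half the 25 mg arm switching, within-subject correlation 0.5–0.7.

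| Sites (assumed) | Women | SE ÷ 0.319, equal weights | Power |
|---|---|---|---|
| 15 near-equal | 50% | 0.96–0.98 | 82–83% |
| 15 near-equal | 65% | 0.99–1.01 | 80–81% |
| 15 near-equal | 80% | 1.11 | 72% |
| Moderate skew (50 down to 8) | 50% | 1.06–1.07 | 75% |
| Moderate skew | 65% | 1.09 | 73% |
| Moderate skew | 80% | 1.18–1.19 | 66% |
| Extreme (137 and fourteen of 8) | 80% | 1.27–1.29 | 59–60% |

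Observed-margin weights give SE ratios of 0.95–0.99 and power of 81–84% over the same scenarios. A week-12-only ANCOVA with those weights gives about 78–79%. The equal-weight SE is 1.00 to 1.34 times the observed-margin SE.

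**4. Offset from baseline.** If 3.562 is the raw SD of change and baseline correlates 0.3–0.5 with change, the residual SD is 3.562 × √(1 − r²) = 3.40 to 3.08. Equal-weight power is then 85–92% with near-equal sites and 50% women, 70–78% with moderate skew and 80% women, and 63–72% in the extreme case.

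**5. Shift in the estimate.** Equal-weight mean minus enrolled-mix mean = Σ(1/K − p_k) × site effect + (0.5 − f) × sex effect, where p_k is the share of subjects at site k. With f = 0.8 and an assumed sex difference of 0.5 micturitions, the sex term has size 0.3 × 0.5 = 0.15, one-sixth of the 0.9 design effect. It is zero if sex has no effect on change.

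**The case against.** The strongest reply is that nothing in the SAP says the weights are equal. That stands: equal weighting is an inference from a software default, and the defect is that the weights are unspecified.

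A reader might also infer that the trial does not deliver its 80% power. The documents do not support that. They give neither site sizes nor sex split, and with near-equal sites and up to 65% women the MMRM keeps 80–83%. The South China survey in Protocol 2.2 (18.0% of men, 28.7% of women) would imply 28.7/(28.7 + 18.0) = 61% women if cases enrolled in proportion to prevalence and the sexes were equally numerous. That is inside the harmless range when sites are similar. Partial data from dropouts and the baseline covariate also help.

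Nor does the LS mean describe a population that was not enrolled. It reweights enrolled subjects, and it differs from their simple mean only if site or sex affects the change.

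There is mitigation too. Very small sites are pooled, and SAP 6.4.1.2 plots unadjusted means beside the LS means. A larger, correctly estimated SE does not inflate type I error.

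These points limit the size of the problem but do not remove it. The pooling rule itself anticipates unequal sites, no sex quota or stratification by sex appears in the eligibility or randomization text, and the unadjusted plots do not supply the primary p-value. In none of the scenarios did equal weighting give a materially smaller SE than observed margins.

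**Conclusion.** The point holds as a conditional one. The primary estimator is under-specified in a setting where the weights matter, and the usual default departs from both the subject-level estimand and the simple-mean sizing.

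The cost ranges from nothing (near-equal sites, up to 65% women) through 66–75% power (moderate site skew or 80% women) to about 60% in an extreme layout. These figures are at SD 3.562 and rest on assumed site sizes, sex split, switching rate and within-subject correlation. Adjustment for baseline could recover part of the loss. Observed-margin weights hold power at about 78–84% in every layout tried. The change is worth making before lock, but it is no ground for saying that the trial is underpowered or its test invalid.

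**What to change.** Add to SAP 6.4.1.1 and 6.4.2 that LS means are averaged over the observed sex and pooled-site distribution of FAS subjects, with one record per subject. For example, compute observed margins from a one-row-per-subject FAS data set. The one-row rule matters because margins taken from the repeated-measures records would give dropouts and switchers less weight. Leave the model otherwise unchanged.

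The cost is a sentence in each section and one program option; SAP 1 allows revisions before hard lock. The downside is that the LS means then depend on the enrolled site and sex mix.
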